8.1. Efficacy Assessments

Site personnel who are to be involved in performing the efficacy assessments must be experienced in the use of the various scales and questionnaires.

To ensure consistency of ratings on each efficacy measure for each participant during the study, the same rater should perform the assessments where possible.

Wherever possible the NRS, part IB and II of the MDS-UPDRS, the HADS and the PGI-C should be completed by the participant. However, in the case of the participant's incapacity, for example due to dyskinesia, tremor, etc., the participant's caregiver may complete the NRS, part IB and II of the MDS-UPDRS, the HADS and the PGI-C based on information reported by the participant.

The following parameters are to be completed by the rater:

- MDS-UPDRS (part IA, III and IV).
- CGI-S.
- CGI-C.

8.1.1. Pain Assessments

The primary efficacy endpoint for the study is the mean change in pain severity ("average pain experienced in the last 7 days"), as assessed by an 11-point NRS, from baseline to week 16.

Pain severity data will be derived from the daily diary.

Daily Diary

An electronic diary will be completed daily by each participant as follows:

- to record the PD pain score at screening (Visit 1), by completion of an 11-point NRS, to confirm eligibility
- the NRS score is calculated over 7 consecutive days immediately prior to baseline (Visit 2/Day 1) and Visits 3, 4 and 5/EOT/ET (Weeks 4, 8 and 16), completion of an 11-point NRS, to allow for the assessment of the average pain experienced in the last 7 days during which patient records on a daily basis the most severe pain using an 11-point NRS.
- on a daily basis from baseline onwards, an accurate record of the use of PRN pain medication for PD-associated pain (Section 10.1.6.2).

Daily Diary Training

At the screening visit, the Investigator (or other trained, qualified personnel) will reinforce recognition of PD-related chronic pain, as well as the use of the daily diary.

On each visit, the Investigator will instruct the participant to complete the daily diary at home for the 7 consecutive days immediately prior to the next visit.

Participants will record the intensity of their PD-associated pain, as the worst pain experienced over the past 24 hours, (from 0 [no pain] to 10 [worst possible pain]) using an 11-point NRS. Pain intensity should be recorded if possible, in the evening before going to sleep. If the subject suffered from more than 1 PD-associated pain, the more severe pain will be documented.

8.2. Safety Assessments

Planned time points for all safety assessments are provided in the SoA.

8.2.1. Physical Examinations

- A complete physical examination will include, at a minimum, assessments of the general appearance, head, ears, eyes, nose, throat, neck, skin, cardiovascular system, respiratory system, abdominal system and nervous system.
- Investigators should pay special attention to clinical signs related to previous serious illnesses.

8.2.2. Vital Signs

Blood pressure and heart rate will be assessed in the supine position with a completely automated device. Manual techniques will be used only if an automated device is not available.

Measurement should be preceded by at least 5 minutes of rest for the participant in a quiet setting without distractions (e.g., television, cell phones).

8.2.3. Cognitive Impairment

Participants will be evaluated for cognitive impairment using the MMSE. The MMSE (Folstein et al, 1975) is a brief practical screening test for cognitive dysfunction. The test consists of 5 sections (orientation, registration, attention and calculation, recall, and language) and has a total possible score of 30. It will be used as a quick method to assess the severity of cognitive dysfunction. The MMSE will be used for screening participants (a total score < 24 is exclusionary).

8.2.4. Clinical Safety Laboratory Assessments

- See Appendix 2 for the list of clinical laboratory tests to be performed and to the SoA for the timing and frequency.
- The investigator must review the laboratory report, document this review, and record any clinically relevant changes occurring during the study both in the appropriate section of eCRF study's visit and in the AE section of the eCRF. The laboratory reports must be filed with the source documents. Clinically significant abnormal laboratory findings are those which are not associated with the underlying disease, unless judged by the investigator to be more severe than expected for the subject's condition.
- All laboratory tests with values considered clinically significantly abnormal during participation in the study or within 2 weeks after the last dose of study intervention should be repeated until the values return to normal or baseline or are no longer considered clinically significant by the investigator or medical monitor.
 - If such values do not return to normal/baseline within a period of time judged reasonable by the investigator, the etiology should be identified and the sponsor notified.
 - All protocol-required laboratory assessments, as defined in Appendix 2, must be conducted in accordance with the laboratory manual and the SoA.
 - If laboratory values from non-protocol specified laboratory assessments performed at the institution's local laboratory require a change in participant management or are considered clinically significant by the investigator (eg, SAE or AE or dose modification), then the results must be recorded in the CRF.

8.2.5. Suicidal Risk Monitoring

Not applicable.

8.3. Adverse Events and Serious Adverse Events

The definitions of an AE or SAE can be found in Appendix 3.

AE will be reported by the subject (or, when appropriate, by a caregiver, surrogate, or the participant's legally authorized representative).

The investigator and any qualified designees are responsible for detecting, documenting, and recording events that meet the definition of an AE or SAE and remain responsible for following up AEs that are serious, considered related to the study intervention or study procedures, or that caused the participant to discontinue the study (see Section 7)

8.3.1. Time Period and Frequency for Collecting AE and SAE Information

All (S)AEs will be collected from the signing of the informed consent form (ICF) until the follow-up call at the time points specified in the SoA (Section 1.3).

All SAEs will be recorded and reported to the sponsor or designee within 24 hours, as indicated in Appendix 3. The investigator will submit any updated SAE data to the sponsor within 24 hours of it being available.

Investigators are not obligated to actively seek AE or SAE after conclusion of the study participation. However, if the investigator learns of any SAE, including a death, at any time after a participant has been discharged from the study, and he/she considers the event to be reasonably related to the study intervention or study participation, the investigator must promptly notify the sponsor.

The method of recording, evaluating, and assessing causality of AE and SAE and the procedures for completing and transmitting SAE reports are provided in Appendix 3.

8.3.2. Method of Detecting AEs and SAEs

Care will be taken not to introduce bias when detecting AEs and/or SAEs. Open-ended and non-leading verbal questioning of the participant is the preferred method to inquire about AE occurrences.

8.3.3. Follow-up of AEs and SAEs

After the initial AE/SAE report, the investigator is required to proactively follow each participant at subsequent visits/contacts. All SAEs will be followed until resolution, stabilization, the event is otherwise explained, or the participant is lost to follow-up (as defined in Section 7.3). Further information on follow-up procedures is given in Appendix 3.

8.3.4. Regulatory Reporting Requirements for SAEs

- Prompt notification by the investigator to the sponsor of a SAE is essential so that legal obligations and ethical responsibilities towards the safety of participants and the safety of a study intervention under clinical investigation are met.
- The sponsor has a legal responsibility to notify both the local regulatory authority and other regulatory agencies about the safety of a study intervention under clinical investigation. The sponsor will comply with country-specific regulatory requirements relating to safety reporting to the regulatory authority, Institutional Review Boards (IRB)/Independent Ethics Committees (IEC), and investigators.
- Investigator safety reports must be prepared for suspected unexpected serious adverse reactions (SUSAR) according to local regulatory requirements and sponsor policy and forwarded to investigators as necessary.
- An investigator who receives an investigator safety report describing a SAE or other specific safety information (e.g., summary or listing of SAEs) from the sponsor will review and then file it in the Investigator Study File and will notify the IRB/IEC, if appropriate according to local requirements.
- The reference safety information for this study is the Summary of Product Characteristics of Safinamide

8.3.5. Pregnancy

- Details of all pregnancies in female will be collected after the start of study intervention and until 1 month after the last dose of study drug
- If a pregnancy is reported, the investigator should inform the sponsor within 24 hours of learning of the pregnancy and should follow the procedures outlined in Appendix 4.
- Abnormal pregnancy outcomes (e.g., spontaneous abortion, fetal death, stillbirth, congenital anomalies, ectopic pregnancy) are considered SAEs.

8.3.6. Disease-Related Events and/or Disease-Related Outcomes Not Qualifying as AEs or SAEs

Not applicable

8.4. Treatment of Overdose

The anticipated pattern of events or symptoms following intentional or accidental overdose with safinamide is that related to its pharmacodynamic profile (MAO-B inhibition with activity dependent inhibition of sodium channels). The symptoms of excessive MAO-B inhibition (increase in dopamine level) could include hypertension, postural hypotension, hallucinations, agitation, nausea, vomiting and dyskinesia.

There is no known antidote to safinamide or any specific treatment for a safinamide overdose. If a significant overdose should occur, safinamide treatment should be discontinued and supportive treatment should be administered as clinically indicated.

In the event of an overdose, the Investigator should:

1. Contact the Medical Monitor immediately.
2. Closely monitor the participant for any AE/SAE or laboratory abnormalities
3. Obtain a plasma sample for PK analysis if requested by the Medical Monitor (determined on a case-by-case basis).
4. Document the quantity of the excess dose as well as the duration of the overdose in the CRF.

Decisions regarding dose interruptions or modifications will be made by the investigator in consultation with the Medical Monitor based on the clinical evaluation of the participant.

8.5. Pharmacokinetics

PK parameters are not evaluated in this study.

8.6. Pharmacodynamics

Pharmacodynamic parameters are not evaluated in this study.

8.7. Genetics

Genetics are not evaluated in this study.

8.8. Biomarkers

Biomarkers are not evaluated in this study.

8.9. Health Economics

Health Economics are not evaluated

9. Statistical Considerations

9.1. Statistical Hypotheses

The null hypothesis is that safinamide is not able to reduce pain severity compared to placebo.

9.2. Sample Size Determination

On the basis of previous post-hoc analyses of pain (Cattaneo et al 2017) and of similar studies (Folstein et al, 1975), it is anticipated that a sample size of 144 participants would permit detection of a 1 point treatment difference in the NRS between safinamide and placebo assuming a standard deviation of 2, 5% significance and 80% power. A 1 point treatment difference is considered to be a clinically meaningful treatment effect (Rascol et al, 2016).

Approximately 220 participants will be screened to achieve 177 randomly assigned to study intervention and of which approximately 144 participants complete the study (96 and 48 evaluable participants in the active and placebo group respectively).

Since March 2020, the COVID-19 emergency has impacted the feasibility of the trial, which is being conducted in a vulnerable group of patients. Upon receipt of the guidance “Statistical Considerations for Clinical Trials During the COVID-19 Public Health Emergency” issued by FDA on June 2020, released with the aim of helping sponsors ensure that trials conducted during the Covid-19 emergency could continue, where appropriate, to provide interpretable findings with correct statistical quantification of uncertainty, the Sponsor performed a Blind Data Review Analysis of the primary endpoint data (pain severity) for the 26 patients who had completed the study as of June 2020.

The results of the analysis show that the standard deviation used in the original sample size estimation (SD = 2. was a conservative overestimate of the observed SD from the actual trial data, which is 1.43.

Based on this, the Standard Deviation, for the estimation of sample size has now been amended to 1.50, and the power has been maintained as 80%. New sample size estimates have been performed considering different magnitudes of Treatment Difference, but keeping the same assumptions of screen failure rates and drop out rates. These are summarized below in Table below

| SCENARIO | SAMPLE SIZE |
|--|---|
| Power = 80% Standard deviation = 1.5 Treatment Difference = 1 point | Pts to screen= 132 Pts to randomize= 105 Pts completing study= 84 |
| Power = 80% Standard deviation = 1.5 Treatment Difference = 1.5 points | Pts to screen= 66 Pts to randomize= 51 Pts completing study= 39 |
| Power = 80% Standard deviation = 1.5 Treatment Difference = 2 points | Pts to screen= 39 Pts to randomize= 30 Pts completing study= 24 |

It is now planned to keep the initial conservative estimate of treatment difference as 1 and change the SD to 1.5 in line with what was observed with the Blind Data Review Analysis. Using these parameters, up to 132 participants will be screened to achieve up to 105 randomized, to have approximately 84 patients complete the study (56 in the active and 28 in the placebo group respectively).

However, given the continuous and uncertain impact that COVID-19 outbreak is having in the countries participating in the trial, any of other scenarios might be adopted if at the end of December 2020 the above enrollment goal will not be achieved. From the table above it can be seen that if the treatment difference is greater than 1, statistical significance can be achieved with a substantially lower sample size. Thus, the study maintains its robustness.

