4.1. Sample Size

On the basis of previous post-hoc analyses of pain (Cattaneo et al 2017) and of similar studies ([Folstein et al, 1975](#)), assuming a standard deviation of 2 it is anticipated that a sample size of 144 subjects would permit detection of a 1 point treatment difference in the NRS between safinamide and placebo at the 5% significance level with 80% power. A 1-point treatment difference is considered to be a clinically meaningful treatment effect ([Rascol et al, 2016](#)).

Approximately 220 subjects will be screened to achieve approximately 177 randomly assigned to study treatment and of which approximately 144 subjects completing the study (n= 96 and n= 48 evaluable subjects in the active and placebo group respectively).

Since March 2020, the COVID-19 emergency has impacted the feasibility of the trial, which is being conducted in a vulnerable group of patients. Upon receipt of the guidance “Statistical Considerations for Clinical Trials During the COVID-19 Public Health Emergency” issued by FDA on June 2020, released with the aim of helping sponsors ensure that trials conducted during the Covid-19 emergency could continue, where appropriate, to provide interpretable findings with correct statistical quantification of uncertainty, the Sponsor performed a Blind Data Review Analysis of the primary endpoint data (pain severity) for the 26 patients who had completed the study as of June 2020.

The results of the analysis show that the standard deviation used in the original sample size estimation (SD = 2) was a conservative overestimate of the observed SD from the actual trial data, which was 1.43 at the time of the blinded data review.

Based on this, the Standard Deviation, for the estimation of sample size has now been amended to 1.50, and the power has been maintained as 80%. New sample size estimates have been performed considering different magnitudes of Treatment Difference but keeping

the same assumptions of screen failure rates and dropout rates. These are summarized below in [Table 4.1](#).

Table 4.1 Sample Size Estimations

SCENARIO	SAMPLE SIZE
Power = 80% Standard deviation = 1.5 Treatment Difference = 1 point	Pts to screen= 132 Pts to randomize= 105 Pts completing study= 84
Power = 80% Standard deviation = 1.5 Treatment Difference = 1.5 points	Pts to screen= 66 Pts to randomize= 51 Pts completing study= 39

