Power = 80% Standard deviation = 1.5 Treatment Difference = 2 points	Pts to screen= 39 Pts to randomize= 30 Pts completing study= 24

Currently, it is planned to keep the initial conservative estimate of treatment difference as 1 and change the SD to 1.5 in line with what was observed with the Blind Data Review Analysis. Using these parameters, up to 132 participants will be screened to achieve up to 105 randomized, to have approximately 84 patients complete the study (56 in the active and 28 in the placebo group respectively).

However, given the continuous and uncertain impact that COVID-19 outbreak is having in the countries participating in the trial, any of other scenarios might be adopted if at the end of December 2020, the above enrollment goal will not be achieved. From the table above it can be seen that if the treatment difference is greater than 1, statistical significance can be achieved with a substantially lower sample size. Thus, the study maintains its robustness.

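### The COVID-19 fallback to 39 or 24 completers is called robust, but for the retained 1-point difference its power is about 48% or 31% on the plan's own sizing basis

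*Protocol*

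**What the plan says.** Protocol 9.2 sets the clinical benchmark first: "A 1 point treatment difference is considered to be a clinically meaningful treatment effect". The 2020 re-sizing rests on a blinded review of pain severity "for the 26 patients who had completed the study as of June 2020". That review gave an SD which SAP 4.1 describes as one "which was 1.43 at the time of the blinded data review". The decision was to "keep the initial conservative estimate of treatment difference as 1 and change the SD to 1.5", giving 84 completers (56 active, 28 placebo).

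The table in both documents adds two smaller rows. One is headed "Power = 80% Standard deviation = 1.5 Treatment Difference = 1.5 points" and needs 51 randomised and 39 completers. The other assumes 2 points and needs 30 randomised and 24 completers. Protocol 9.2 then says that "any of other scenarios might be adopted if at the end of December 2020 the above enrollment goal will not be achieved", and SAP 4.1 repeats it. The stated justification is "if the treatment difference is greater than 1, statistical significance can be achieved with a substantially lower sample size. Thus, the study maintains its robustness".

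Neither document states the power for a 1-point difference at 39 or 24 completers.

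**The concern.** The argument starts from a condition (the true difference exceeds 1 point) and ends in an unconditional statement about the study. The smaller sizes would be triggered by an enrolment shortfall, which carries no information about the treatment effect. The June 2020 review was blinded and is reported only as an SD, so it cannot support a larger difference either. Meanwhile the plan keeps 1 point and calls that value conservative.

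If a smaller scenario is adopted, the sample-size sections would claim robustness for a trial that has about an even chance (39 completers), or less than that (24), of detecting the difference they call clinically meaningful. A non-significant result would then say little about whether a 1-point effect exists, and a reader relying on the stated robustness could take it as evidence against one.

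**Working it through.** **Inputs.** Difference 1 point, SD 1.5, 5% significance, 80% power, and completers 84, 39 and 24 (Protocol 9.2, SAP 4.1); allocation 2:1 (Protocol 4.1). The 26:13 and 16:8 splits follow from 2:1. The documents do not name the sizing test or its sidedness, so the first step is to identify it.

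**Formulas.** With n1 active and n2 placebo completers:
- SE = SD × √(1/n1 + 1/n2)
- noncentrality δ = difference / SE
- two-sided power = P(|T| > t(0.975, N−2)), where T is noncentral t with N−2 degrees of freedom and noncentrality δ
- expected 95% CI half-width = t(0.975, N−2) × SE, with the SD at its planning value

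**Step 1: reproduce the plan's sizes.** Take the smallest multiple of 3 with power of at least 80%.

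| Difference | SD | Stated completers | Power there | Power with 3 fewer |
|---|---|---|---|---|
| 1 | 2 | 144 | 80.2% | 79.4% |
| 1 | 1.5 | 84 | 81.2% | 79.8% |
| 1.5 | 1.5 | 39 | 81.8% | 78.5% |
| 2 | 1.5 | 24 | 83.7% | 78.0% |

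All four sizes come out exactly. A one-sided 5% t-test gives 114, 66, 30 and 18. The normal approximation gives 144, 81, 36 and 21. The basis is therefore an unadjusted two-sided t-test on completers.

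**Step 2: power for 1 point at each size (SD 1.5).**

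| Completers | SE | δ | t(0.975) | Power | Half-width | Difference with 80% power |
|---|---|---|---|---|---|---|
| 84 (56:28) | 0.347 | 2.88 | 1.989 | 81% | 0.69 | 0.98 |
| 39 (26:13) | 0.509 | 1.96 | 2.026 | 48% | 1.03 | 1.47 |
| 24 (16:8) | 0.650 | 1.54 | 2.074 | 31% | 1.35 | 1.90 |

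For 39: SE = 1.5 × √(1/26 + 1/13) = 0.509 and δ = 1/0.509 = 1.96. The half-width is also the smallest observed difference that reaches p < 0.05. At SD 1.5, an observed difference of exactly 1 point would therefore miss significance at both smaller sizes.

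**Step 3: more favourable assumptions, true difference 1 point.** The 25% variance reduction from baseline adjustment is an assumption; the documents give no figure.

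| Assumption | 39-completer scenario | 24-completer scenario |
|---|---|---|
| Completers, SD 1.5 | 48% | 31% |
| Completers, SD 1.43 | 52% | 34% |
| All randomised (51 or 30) contribute fully, SD 1.5 | 60% | 38% |
| All randomised, SD 1.43 | 64% | 41% |
| Completers, SD 1.5, 25% less variance | 60% | 40% |
| All randomised, SD 1.5, 25% less variance | 72% | 48% |

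**Step 4: dates.** The blinded review already had 26 completers in June 2020. Amendment 2.0 is dated 27 October 2020. The 24-completer row had thus been passed before the amendment offered it. At 26 completers (17:9 split assumed, SD 1.5), power for 1 point is 34% and the half-width 1.28.

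**The case against.** The best defence is that much of this is visible. Each table row prints its assumed difference, the plan says 84 for 1 point, the sentence before the conclusion is conditional, and the fall-back is only permitted. That is all true, and the table is correct. It does not rescue the conclusion, which drops the condition and is what justifies the smaller sizes.

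Second, the primary analysis is not a t-test on completers. It is an MMRM on the full analysis set with baseline pain as covariate, so 48% and 31% lie at the low end. This stands, and Step 3 shows how far it might go. One further allowance is possible: if 1.43 was pooled over arms and the true difference is 1 point, the within-arm SD is √(1.43² − (2/3)(1/3) × 1²) = 1.35, which gives about 57% at 39 completers. Only by stacking everything (SD 1.35, all 51 randomised fully informative, 25% less variance) does power reach about 81%, and the 24-completer scenario stays well short. The plan makes none of these assumptions: it sizes on completers at SD 1.5, and an SD from 26 patients can err in either direction.

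Third, 24 can no longer be the final number of completers. That is correct, so 39 is the figure that matters most in practice. The documents still list the 24 row as one that might be adopted.

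Fourth, the 95% CI required by SAP 10.1 will show the imprecision. It will, but only afterwards; the sample-size sections make their claim beforehand.

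**Conclusion.** The concern holds and should be fixed. For the difference the plan retains, the fall-back has 48% power at 39 completers and 31% at 24, against 81% at 84. At SD 1.5, 80% power is reached only for true differences of about 1.47 and 1.90 points. These figures rest on an unadjusted two-sided 5% t-test on completers, 2:1, SD 1.5. That basis is inferred, but it matches all four stated sizes. The MMRM may do better by an amount the documents do not quantify. At the planning SD, the most favourable case in Step 3 gives 72% and 48%.

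The fault lies in the claim made for the contingency. Type I error, the treatment estimate and the table's arithmetic are not in question, and the point bites only if a smaller scenario is adopted.

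**What to change.** In Protocol 9.2 and SAP 4.1, delete the concluding robustness sentence and put in its place wording such as:

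> If a smaller scenario is adopted, 80% power holds only for a true difference of about 1.5 points (39 completers) or about 1.9 points (24 completers). For the retained 1-point difference, power is about 48% (expected 95% CI half-width about 1.03 points) at 39 completers and about 31% (about 1.35 points) at 24, on the unadjusted two-sided t-test and completer basis used for sizing.

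The sponsor should confirm that sizing basis before the text is adopted. It may add that the MMRM is expected to be more efficient, provided it states the assumed gain.

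Cost: one sentence replaced in each document, with no extra patients, no change to the analysis and no bar on the contingency. The downside is that the stated power for an early close looks less favourable.
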